#### **5.3.** Dose Selection

[figure not shown]
#### 5.3.1. Pembrolizumab

The pembrolizumab dose of 200 mg Q3W is the approved dose for the treatment of patients with HNSCC (Keytruda USPI).

#### 5.3.2. ALKS 4230

All patients in this study will be given ALKS 4230 at a daily dose of 3  $\mu$ g/kg for 5 consecutive days on Days 1 through 5 of the first week of each 3-week treatment cycle.

A first-in-human (FIH) clinical study with ALKS 4230 has been initiated and is currently ongoing (ALK4230-A101). This study is being conducted in patients with advanced solid tumors who are refractory or intolerant to therapies known to provide clinical benefit. Patients are administered ALKS 4230 by a 30-minute intravenous (IV) infusion daily for 5 days followed by an off-treatment period (as described in the ALK4230-A101 protocol) in repeating cycles. Dosing is repeated every 21 days, except during the first treatment cycle, which is 14 days.

## 6. STUDY OBJECTIVES

#### 6.1. **Primary Objective**

The primary objective of this study is to estimate the response rate to ALKS 4230 in combination with pembrolizumab in patients with HNSCC who have previously received anti-PD-(L)1 therapy but who have not achieved a CR. The primary objective will be assessed for the following 2 groups:

- Group 1: Patients with SD, defined as ≥12 weeks of SD per Response Evaluation Criteria in Solid Tumors (RECIST) v1.1 criteria, or patients with PR with no further reduction in tumor size or response (ie, PR and not improving further) for ≥8 weeks on prior anti-PD-(L)1 therapy
- Group 2: Patients with PD with no prior response to anti-PD-(L)1 therapy after ≥8 weeks on anti-PD-1 therapy or patients currently with PD after prior achievement of a best response of SD or PR and after ≥8 weeks on anti-PD-(L)1 therapy.

## 6.2. Secondary Objectives

- To evaluate the DOR, progression-free survival (PFS), time to progression (TTP), and OS of patients with advanced or recurrent HNSCC receiving pembrolizumab plus ALKS 4230
- To evaluate the safety and tolerability of pembrolizumab plus ALKS 4230

## 6.3. Exploratory Objectives

- To evaluate whether assessment of pretreatment biopsies from patients who have failed to achieve a CR on therapy with anti-PD-(L)1 can identify a subset of patients who are likely to respond to the addition of ALKS 4230
- To evaluate whether a second biopsy, \_\_\_\_\_\_, can identify changes in tumors that will predict response or failure to the addition of ALKS 4230
- ٠

## 7. SELECTION AND WITHDRAWAL OF PATIENTS

Each patient must meet all of the inclusion and none of the exclusion criteria to be qualified to participate in this study.

## 7.1. Patient Inclusion Criteria

- 1. Is  $\geq 18$  years of age.
- 2. Is willing and able to provide informed consent.
- 3. Is willing and able to follow the study procedures as outlined in the protocol.
- 4. Must have a histologically or cytopathologically confirmed diagnosis of HNSCC region that is locally advanced or recurrent and no longer amenable to local surgical or radiation therapy and/or with evidence of metastatic disease. Both HPV-positive and -negative patients will be included.
- 5. Must have had prior PD-1:PD-L1 inhibition therapy with anti-PD-(L)1 therapy as the most recent systemic therapy with
  - a. (Group 1, Cohort 1) current SD (for  $\geq 12$  weeks by RECIST criteria v1.1) or
  - b. (Group 1, Cohort 2) current PR with no further reduction in tumor size or response for ≥8 weeks (ie, PR and not further improving)
  - c. (Group 2, Cohort 3) current PD with no prior response to anti-PD-(L)1 therapy after  $\geq 8$  weeks on anti-PD-(L)1 or
  - d. (Group 2, Cohort 4) current PD after prior achievement of a best response of SD or PR and after ≥8 weeks on anti-PD-(L)1 therapy

Some minimal intervening localized palliative radiotherapy or ablation therapy may be allowed upon review and agreement by the ION and Alkermes Medical Monitors.

- 6. Must have disease that is measurable by RECIST v1.1 criteria as determined by the treating physician and not confounded by prior treatment such as radiation. Patients with only 1 site of disease must be able to provide adequate tissue samples at the time of biopsy that will not affect the tumor size per RECIST v1.1 criteria.
- 7. Patients who have received standard or investigational anti-PD-(L)1 agents as the most recent systemic therapy must wait at least 3 weeks (with the exception of an anti-PD-[L]1 inhibitor that is dosed Q2W and in consultation with the ION and Alkermes Medical Monitors, in which case patients must wait at least 2 weeks) before enrollment into the study or 4 weeks if the half-life of the investigational agent is not known. Patients who have received standard or investigational agents other than anti-PD-(L)1 agents (including agents as part of a combination regimen with an anti-PD-[L]1 agent) must wait 8 weeks before enrollment into the study, unless discussed with and approved by the ION and Alkermes Medical Monitors on an individual basis.
- 8. Patients must be willing to provide tumor tissue adequate for biomarker correlative studies at the time points specified in the protocol.

- 9. Patients should have readily accessible tumor for biopsy pre- and post-pembrolizumab and ALKS 4230 combination regimen. Biopsy should be excisional, incisional, or core needle and large enough to show tissue architecture.
- 10. Have a performance status of ≤2 on the Eastern Cooperative Oncology Group (ECOG) Performance Scale.
- 11. Demonstrate adequate organ function as defined in Table 3. All screening laboratories should be performed within 10 days of treatment initiation.

System	Laboratory Value
Hematological	
ANC	$\geq$ 1,000/µL without hematopoietic growth factor support
Platelet count	≥100,000/µL without transfusion support
Hemoglobin	$\geq 9 \text{ g/dL}$
Renal	
Serum creatinine OR	≤1.5×ULN OR
Measured or calculated a CrCl	
(glomerular filtration rate [GFR] can also	≥60 mL/min
be used in place of creatinine or CrCl)	
Hepatic	
	≤1.5×ULN OR
Serum total bilirubin	Direct bilirubin ≤ULN for patients with total bilirubin levels
	>1.5×ULN
AST and ALT	≤2.5×ULN OR
	$\leq$ 5×ULN for patients with liver metastases
Albumin	>2.5 mg/dL
Coagulation	
INR or PT aPTT	
 
≤1.5×ULN unless patient is receiving anticoagulant therapy.
 
If the patient is receiving anticoagulant therapy, the INR or PT needs to be within the therapeutic range of intended use of anticoagulants or deemed a safe level for the proposed biopsies by the biopsy surgeon or interventional radiologist.
 
≤1.5×ULN unless patient is receiving anticoagulant therapy. If the patient is receiving anticoagulant therapy, the aPTT needs to be within the therapeutic range of intended use of anticoagulants or deemed a safe level for the proposed biopsies by the biopsy surgeon or interventional radiologist.
 

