## 5.2. Study Rationale

Although the clinical studies with nivolumab and pembrolizumab have demonstrated antitumor activity and established the efficacy, activity, and benefits with anti-PD-1 therapy in the recurrent metastatic platinum-experienced HNSCC population, the response rates remain low, and the numbers of patients who relapse or fail to achieve CR remain in the high majority of 85% or more. As patients with HNSCC suffer tremendous morbidity and mortality with this disease, and the efficacy of any single-agent chemotherapy remains low with no proven salvage options in this population that fails anti PD-1 therapy, there is an exceptionally high unmet need to discover new therapies or effective combination immunotherapy to enhance, improve, or restore the responses to anti-PD-1 therapy.

This study (ION-01-ALKS4230) will enroll patients who have received prior anti-PD-1 antibody therapy (pembrolizumab or nivolumab) as their last treatment or those receiving ongoing current anti-PD-1 antibody therapy who have not achieved a CR. Programmed cell death protein-1:programmed cell death ligand-1 (PD-L1) (henceforth referred to as PD-[L]1) inhibitors are effective in small subsets of virtually every histologic type of cancer, yet most treated patients fail to benefit. Moreover, many of the tumors that respond eventually relapse. Therefore, it is highly likely that, in the near future, patients with stable disease (SD) or progressing on anti-PD-(L)1 therapy will likely be the largest single category of patients in the US. In the long-term follow-up analysis of the KEYNOTE-012 study of single agent pembrolizumab conducted in 192 patients with HNSCC, the objective response rate was 18% (95% CI, 13% to 24%) (Mehra et al, 2018). Among the subset of patients achieving a response, the median time to best response

was 2 months (range, 2 to 17 months).

Discerning the character of the tumors in patients who are not achieving complete regression on PD-(L)1 inhibition with anti-PD1 or anti-PD-L is essential. Thus, pretreatment biopsies will be mandated. At present, the tumors most likely to respond to anti-PD-1 are those with an increased number of mutations and thus abnormal proteins containing potentially immunogenic epitopes and infiltration of T cells capable of recognizing the abnormal proteins. Mechanisms by which tumors fail to respond to anti-PD-1 are not yet comprehensively defined

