While it is not currently possible to hypothesize the frequency or proportion of each mechanism, we believe that biopsies from participants prior to and during therapy will provide insight into purported mechanisms of failure or success to generate hypotheses that will provide the foundation for future study design.

Assessment of whether addition of ALKS 4230 can induce remission for patients with tumors that do not respond to anti-PD-1 treatment is the essential goal of the study. Understanding whether ALKS 4230 alters the number of NK cells and T cells within tumors is also critical. Thus, the post-treatment (second) biopsy will be collected during Week 2 (Cycle [C] 1, Day [D] 12 or at any time from C1D8 through C1D19).

The study population designates patients with advanced or recurrent HNSCC who are either refractory and progressive on prior anti-PD-(L)1 therapy or have failed to obtain response or tumor regression to anti-PD-1 therapy for more than 8 weeks to receive ALKS 4230 in combination with pembrolizumab. Patients in this population are as follows:

Group 1 (Cohorts 1 and 2) will consist of all patients with current SD (for at least 12 weeks) or partial response (PR) with no further reduction in tumor size or response for  $\geq 8$  weeks (ie, PR and not further improving).

Group 2 (Cohorts 3 and 4) will consist of patients with progressive disease (PD) with no prior response to anti-PD-(L)1 therapy after  $\geq 8$  weeks on anti-PD-(L)1 or current PD after prior achievement of a best response of SD or PR and after  $\geq 8$  weeks on anti-PD-(L)1 therapy.

HNSCC was chosen due to the high unmet need in this difficult-to-treat patient population with no effective therapeutic options for a number of reasons: 1) the demonstrated efficacy and recent approval of pembrolizumab for previously platinum-experienced recurrent or metastatic HNSCC, 2) the ease of serial biopsies in easily accessible sites of tumor in a proportion of patients, and 3) the responses to the combination of ALKS 4230 and pembrolizumab being

readily and easily assessable. However, if efficacy or response is observed, the combination could be tested in many different cancers.

This study will be performed in collaboration with the Immune Oncology Network (ION), who will perform activities related to, but not limited to, oversight and management of clinical sites, medical monitoring, and laboratory analysis services.

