## 8. STUDY DESIGN

#### 8.1. Overall Study Design and Plan

The study will assess the antitumor efficacy of ALKS 4230 in combination with pembrolizumab in patients with advanced, recurrent, and/or HNSCC on treatment with an anti-PD-(L)1 antibody (pembrolizumab or nivolumab) without having achieved a CR.

The study is a multi-center, Phase 2, open-label therapy study in collaboration with ION. Patients must have received anti-PD-(L)1 therapy prior to enrollment into the study. After enrollment in the study, ALKS 4230 with pembrolizumab will be administered to 4 cohorts of patients with advanced, recurrent, and/or metastatic HNSCC who have received anti-PD-(L)1 therapy whose current response is as follows:

- Cohort 1: SD, defined as  $\geq 12$  weeks of SD per RECIST criteria;
- Cohort 2: PR with no further reduction in tumor size or response for ≥8 weeks (ie, PR and not improving further)
- Cohort 3: PD with no prior response to anti-PD-(L)1 therapy after ≥8 weeks on anti-PD-(L)1, or
- Cohort 4: Current PD after prior achievement of best response of SD or PR and after ≥8 weeks on anti-PD-(L)1 therapy

Patients will be administered the combination of ALKS 4230 and pembrolizumab. For simplification, the 4 cohorts of patients will be combined into 2 arms:

- Group 1 will consist of all patients with current SD or PR (Cohorts 1 and 2) who are not progressing or further demonstrating reductions in tumor size.
- Group 2 will consist of patients with PD (Cohorts 3 and 4).

Baseline tumor biopsy will be required at the time of study entry after screening procedures have been completed and prior to first administration of combination regimen to assess each patient's tumor characteristics in an effort to identify patients with tumors that may have limited pembrolizumab efficacy or potential response to anti-PD-1/ALKS 4230 combination. Tumors will be assessed for quantity and character of tumor-infiltrating T cells and other leukocytes, and for quantitative assessment of PD-L1 expression, gene signatures that correlate with response or lack of response

Patients will also have a post-treatment (second) biopsy at C1D12, or at any time from C1D8 through C1D19, to assess whether the addition of ALKS 4230 to the treatment regimen alters the TME and what changes on therapy (immunopharmacodynamics) predispose to responses to the combination.

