## 11. ASSESSMENT OF EFFICACY

## **11.1. Primary Efficacy Endpoint**

The primary objective of this study is to estimate the response rate to ALKS 4230 in combination with pembrolizumab in patients with HNSCC who have previously received anti-PD-(L)1 therapy but who have not achieved a CR. The primary objective will be assessed for the following 2 groups:

- Group 1: Patients with SD, defined as ≥12 weeks of SD per RECIST v1.1 criteria, or patients with PR with no further reduction in tumor size or response (ie, PR and not improving further) for ≥8 weeks on prior anti-PD-(L)1 therapy
- Group 2: Patients with PD with no prior response to anti-PD-(L)1 therapy after ≥8 weeks on anti-PD-1 therapy or patients currently with PD after prior achievement of a best response of SD or PR and after ≥8 weeks on anti-PD-(L)1 therapy.

The primary efficacy endpoint is the rate of new or improved antitumor response (hereafter referred to as objective improvement) after the addition of ALKS 4230 treatment in patients receiving ongoing anti-PD-1 therapy but who have not achieved a CR.

Antitumor activity will be measured by radiological assessment compared to screening. Antitumor response rate of subsets of patients will be based on disease status (defined by PR, SD, or PD based on RECIST v1.1, determined by tumor imaging scans) at screening.

[figure not shown]
An objective improvement for patients within Group 1 (Cohorts 1 and 2) is defined as:

- SD at screening that improves to PR or CR
- PR at screening that improves to CR

An objective improvement for patients within Group 2 (Cohorts 3 and 4) is defined as:

• PD at screening that improves to PR or CR

Baseline scans must be completed within 28 days before the start of treatment. Scans are to be completed according to the time points indicated in the Schedule of Assessments (Table 4). Patients whose response converts from PD or SD to PR or from PR to CR will have a confirmatory scan for tumor assessments 6 weeks after the response-defining scan. Thereafter, timing of tumor assessments will depend on whether or not the patient continues with study drug.

Patients may receive study drug while waiting for confirmation of PD if they are clinically stable as defined by the following criteria:

- Absence of signs and symptoms (including worsening of laboratory values) indicating disease progression
- No decline in ECOG Performance Status
- Absence of rapid progression of disease

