1.2. Summary of the Study Design

The study will assess the antitumor efficacy of ALKS 4230 in combination with pembrolizumab in patients with advanced, recurrent, and/or HNSCC on treatment with an anti-PD-(L)1 antibody (pembrolizumab or nivolumab) without having achieved a CR.

The study is a multi-center, Phase 2, open-label therapy study in collaboration with ION. Patients must have received anti-PD-(L)1 therapy prior to enrollment into the study. After enrollment in the study, ALKS 4230 with pembrolizumab will be administered to 4 cohorts of patients with advanced, recurrent, and/or metastatic HNSCC who have received anti-PD-(L)1 therapy whose current response is as follows:

- Cohort 1: SD, defined as ≥ 12 weeks of SD per RECIST criteria
- Cohort 2: PR with no further reduction in tumor size or response for ≥8 weeks (ie, PR and not improving further)
- Cohort 3: PD with no prior response to anti-PD-(L)1 therapy after ≥8 weeks on anti-PD-(L)1
- Cohort 4: Current PD after prior achievement of best response of SD or PR and after ≥8 weeks on anti-PD-(L)1 therapy

Patients will be administered the combination of ALKS 4230 and pembrolizumab. For simplification, the 4 cohorts of patients will be combined into 2 arms:

- Group 1 will consist of all patients with current SD or PR (Cohorts 1 and 2) who are not progressing or further demonstrating reductions in tumor size.
- Group 2 will consist of patients with PD (Cohorts 3 and 4).

Baseline tumor biopsy will be required at the time of study entry after screening procedures have been completed and prior to first administration of combination regimen to assess each patient's tumor characteristics in an effort to identify patients with tumors that may have limited pembrolizumab efficacy or potential response to anti-PD-1/ALKS 4230 combination. Tumors will be assessed for quantity and character of tumor-infiltrating T cells and other leukocytes, and for quantitative assessment of PD-L1 expression, gene signatures that correlate with response or lack of response Patients will also have a post-treatment (second) biopsy at C1D12, or at any time from C1D8 through C1D19, to assess whether the addition of ALKS 4230 to the treatment regimen alters the TME and what changes on therapy (immunopharmacodynamics) predispose to responses to the combination.

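### Group 1 is described as no longer shrinking, but the Cohort 1 entry criterion does not require this, so continuing shrinkage on anti-PD-(L)1 therapy can be counted as objective improvement

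*Protocol*

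**What the plan says.** Protocol 8.1 defines Group 1 as "all patients with current SD or PR (Cohorts 1 and 2) who are not progressing or further demonstrating reductions in tumor size". SAP 1.2 repeats the condition: "who are not progressing or further demonstrating reductions in tumor size". The rationale in Protocol 5.2 points the same way for patients who are not progressing: they "have failed to obtain response or tumor regression to anti-PD-1 therapy for more than 8 weeks".

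Patients are enrolled on the numbered criteria in Protocol 7.1. Criterion 5b carries a plateau condition: "Group 1, Cohort 2) current PR with no further reduction in tumor size or response for" at least 8 weeks. Criterion 5a carries none. It reads "Group 1, Cohort 1) current SD (for" at least 12 weeks by RECIST v1.1 and stops there. The Cohort 1 wording in the Synopsis, Protocol 6.1, 8.1 and 11.1, and SAP 1.1.1, 1.2 and 1.3.1 also asks only for SD of that duration. In the objectives, the parenthesis that explains the plateau refers to PR alone.

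For Cohort 1, the primary endpoint counts "SD at screening that improves to PR or CR" (Protocol 11.1; SAP 3.11.2). The reference is the study baseline: "Antitumor activity will be measured by radiological assessment compared to screening". Pembrolizumab continues throughout (8.1) and there is no randomization (9.3). Section 8.3.3 asks sites to collect RECIST measurements from the prior anti-PD-(L)1 treatment, but no eligibility or analysis rule uses them.

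**The concern.** Under Protocol 8.3.10.4, SD covers any fall too small to be PR. A patient whose sum has been falling steadily by less than 30% meets 5a, yet lies outside Group 1 as Section 8.1 describes it. The population enrolled and the population described can therefore differ.

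The difference bears on the primary endpoint, which is worded as new or improved response after ALKS 4230 is added. With pembrolizumab continuing and no control arm, evidence that the tumor had stopped shrinking before entry is one of the main reasons to credit a later SD-to-PR change to the added drug. Criterion 5b provides that evidence for PR patients; 5a does not provide it for SD patients. Conversions that would have happened on pembrolizumab alone can then raise the Group 1 rate.

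**Working it through.** **The plan's own reference figure.** Protocol 13.1 and SAP 2 cite 18% (95% CI 13% to 24%) in 192 patients on pembrolizumab alone. Exact Clopper-Pearson intervals agree: 34/192 = 17.7% (12.6% to 23.9%) and 35/192 = 18.2% (13.0% to 24.4%). Protocol 5.2 adds that among responders the median time to best response "was 2 months (range, 2 to 17 months"). Responses on pembrolizumab alone can therefore develop or deepen after 12 weeks, though at least half had reached their best by about 2 months.

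**How far an SD patient must fall.** PR needs a 30% fall from the study baseline (8.3.10.4), which is the last assessment before the first dose (SAP 3.1). A patient entering at 80% of the pre-treatment sum must reach 0.80 × 0.70 = 56% of it. One entering at 74% must reach 0.74 × 0.70 = 52%. Crossing only the old 30% line is not enough.

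**What continuing trend would suffice.** Assume a constant proportional fall *s* per 6 weeks and scans every 6 weeks (Table 4 footnote s; 8.3.10). PR is reached after ln(0.70)/ln(1 − *s*) intervals.

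- Confirmation comes 6 weeks after the response-defining scan (8.3.10, 8.3.10.5). Treatment lasts at most 17 cycles × 3 = 51 weeks (9.1.2). Confirmation at week 48 therefore needs PR by week 42, the 7th scan.
- Smallest trend: *s* = 1 − 0.70^(1/7) = 5.0% per 6 weeks.
- Over the qualifying 12 weeks this is 1 − 0.70^(2/7) = 9.7%, well inside SD.
- An invented patient at −10%, −18% and −26% on successive scans has *s* = 1 − 0.74^(1/3) = 9.5%. PR takes 3.55 intervals, so it is seen at week 24 and confirmed at week 30.

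Table 5 and Table 7 footnote b give a different schedule: 9 weeks, then every third cycle. At 5% per 6 weeks the 30% line is crossed at 6.95 × 6 = 41.7 weeks, seen at week 45 and confirmed at week 51. The illustration survives, but only just.

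**What a small background rate would do.** The Cohort 1 size is not visible, so assume 20 patients and a pembrolizumab-only conversion rate *b*. The chance of at least one such conversion is 1 − (1 − *b*)^20.

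| *b* (assumed) | Expected conversions | P(at least 1) |
|---|---|---|
| 2% | 0.4 | 33% |
| 5% | 1.0 | 64% |
| 10% | 2.0 | 88% |

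No document gives *b*. The table shows sensitivity and is not an estimate.

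**The case against.** The strongest case on the other side has five parts.

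- **Other guards exist.** Twelve weeks of SD is longer than Cohort 2's 8 weeks and screens out early responders. The new baseline demands a further 30% fall, and a confirmatory scan follows. All of this stands. A reader might infer that a pre-entry plateau is the only protection; the documents do not support that.
- **The 17-month figure is weak.** It is the extreme of a range of times to best response, which may include deepening of an existing response, and the median equals the minimum. Protocol 13.1 relabels it as time to objective improvement, but that does not show SD turning into PR at 17 months. This stands: the figure shows only that late change is possible.
- **The trend is hypothetical.** Nothing in the documents shows constant shrinkage over 42 weeks. This stands, and the calculation is only an illustration. A reader might also take any trend that gives a first PR by week 48 as enough (about 4.4% per 6 weeks), but confirmation would then fall at week 54, after the 51 weeks of treatment.
- **The objective concerns the combination** (Protocol 6.1), so a pembrolizumab contribution is part of the target. This stands only in part, because the endpoint in 11.1 is worded as improvement after ALKS 4230 is added.
- **Section 8.1 groups the cohorts for simplification**, so its wording may be a loose summary, and response is also reported by cohort (13.4.2; SAP 3.11.3). The first part is a reason to reconcile the text. The second isolates Cohort 1 but does not separate shrinking from stable patients within it.

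**Conclusion.** The mismatch between criterion 5a and the Group 1 description is real. Patients still shrinking on anti-PD-(L)1 therapy can enter Cohort 1 and can be counted as objective improvements, and any resulting bias in the Group 1 rate is upward. Group 2 is not affected.

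A reader might go further and infer that such patients are present and make up a known part of the rate. The documents do not support that: the share of late responders is not given, and neither the Cohort 1 size nor any assumed background rate is visible. The 5.0% per 6 weeks figure rests on a constant proportional trend and 6-weekly scans. It shows that an unremarkable SD trajectory can lead to a confirmed PR within the treatment period, and says nothing about how often that happens.

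**What to change.** 1. **Reconcile the text.** Bring criterion 5a and the Cohort 1 definitions (Synopsis, Protocol 6.1, 7.1, 8.1 and 11.1; SAP 1.1.1, 1.2 and 1.3.1) into line with the Group 1 description in Protocol 8.1 and SAP 1.2, so that entry and the stated population agree. Which rule to adopt is for the sponsor.
2. **Prespecify a sensitivity analysis** in the SAP before database lock, using the measurements collected under 8.3.3. Report the Cohort 1 and Group 1 objective improvement rates with and without Cohort 1 patients whose target-lesion sum fell by more than a stated margin over the qualifying 12 weeks, and list patients whose prior measurements are unavailable. A margin of at least 10% is one example. It corresponds to 1 − √0.90 = 5.1% per 6 weeks, close to the 5.0% in the illustration. Flagging any fall between the last two scans would be a poor rule, because symmetric measurement noise alone would flag about half of truly stable patients.

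The cost is one extra table row and possibly a slightly less favourable rate in the restricted analysis. If 5a is tightened, some SD patients become ineligible. The sensitivity analysis asks for no data beyond what 8.3.3 already requests and remains useful if enrollment is complete.
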